5.3. Screening Failures

Screen failures are defined as subjects who consent to participate in the clinical trial, but are not subsequently officially enrolled in the study. A minimum set of information including Demography, Screen Failure details, Eligibility Criteria, and SAEs is required from screen failure subjects in order to report screen failures in a reliable manner, satisfy the requirements for publication defined by the Consolidated Standards of Reporting Trials (CONSORT), and respond to requests of the regulatory authorities.

Subjects that fail screening are eligible to be rescreened up to 3 times as soon as the investigator (or subinvestigator) assesses they may meet study entry criteria. In the rescreening case, the re-exams of the ophthalmology at the rescreening are not required if the investigator judges it appropriate to use the previous screening result (see Table 6).

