 - Screening: anytime after consenting and prior to first dose of study medication (Day 1)
 - Week 12: window from weeks 10-14 (inclusive)
 - End of study: window from weeks 20-24 (inclusive)
 - Early study medication discontinuation or study withdrawal: withdrawal eye exam as close to the last dose as possible. Re-conduct is not required if the exam is conducted within two weeks prior to withdrawal visit.
5. Only for females of reproductive potential.
6. Only at determination of menopausal status in female subjects (Section 5.1.).
7. See Table 7
8. For optional genetic research, informed consent should be obtained before the specimen collection.
9. See Section 7.4.1.
10. For examination at early withdrawal, the specified assessments should be performed as far as possible.
11. In the rescreening case, the previous result of ophthalmology exam at the screening may be used and the ophthalmology exam at the rescreening is not necessary, if the subject meets all of the following criteria and the investigator judges it appropriate.
 - There were no findings that would suggest a repeat ophthalmology exam performed within the next 3 months at the latest screening ophthalmology exam.
 - Subjects had no new eye-related symptoms or complaints since the latest screening ophthalmology exam until rescreening.
 - The latest screening ophthalmology exam was performed within 3 months prior to anticipated Day 1.
12. Exams should be conducted at least one week after ESA treatment.

Table 7 Blood Sampling Schedule for Pharmacokinetics

PK sample	Week 12 ²	Week 24 ²
Blood sampling timing ¹		1, 2, 3, and 4 h after administration of GSK1278863

Subjects must take the study medication in consideration of blood sampling time. Subjects will record the date and time of the last two study medication doses taken prior to blood sampling in the medication diary. Preferably, there should be an interval of at least 12 h between these two doses.

1. Blood sampling should be completed within +/- 30 min of the planned collected time.
2. Blood sampling not performed at this visit may be postponed until the following visits.

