#### • Ophthalmology Exams

The responses to each question will be summarized using number and percentage at each assessment visit. The response will be classified into 'Yes' and 'No'. Ophthalmology exam at screening and at on-therapy will be summarized separately. The number of subjects with worst case after-screening ophthalmology exams (i.e., the response is 'Yes' at least once during whole treatment period, including unscheduled visits) will also be summarized by each question.

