#### 10.3.1. Definitions of Analysis Time Point

Analysis Time Point	Definitions
Screening [1]	Data collected in Screening visit
Day 1 [1]	Data collected in Day 1 visit
Week 4	Data collected in Week 4 visit
Week 8	Data collected in Week 8 visit
Week 12	Data collected in Week 12 visit
Week 16	Data collected in Week 16 visit
Week 20	Data collected in Week 20 visit
Week 24	Data collected in Week 24 visit
Follow-up	Data collected in Follow-up visit

Note: Any unscheduled visit will not be slotted to a particular time point.

[1] For rescreened subjects, data collected in screening-pass visit will be used for analysis. They may have multiple records at Screening and/or Day 1 visit, which associates with a screening-pass visit and screening failure visit(s)

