# **10.6.** Appendix 6: Derived and Transformed Data

### 10.6.1. General

Multiple Measurements at One Time Point			
• Mean of the measurements will be calculated and used in any derivation of summary statistics but if listed, all data will be presented.			
• Subjects having both High and Low values for Normal Ranges at any post-baseline visits for safety parameters will be counted in both the High and Low categories of "Any visit post-baseline" row of related summary tables. This will also be applicable to relevant Potential Clinical Importance summary tables.			
• For multiple measurements at Screening and Day 1 visit, the screening-pass visit record will be used for analysis (See Appendix 3).			
Study Day			

 
Calculated as the number of days from randomization date:
 
Ref Date = Missing → Study Day = Missing
 
Ref Date < Randomization Date → Study Day = Ref Date - Randomization Date → Study Day = Ref Date - (Randomization Date) +1
 
			
Unique Subject ID			

 
All subjects have unique subject ID for analyses even if a subject was enrolled after rescreened. Tables/figures/listings will be produced based on unique subject ID.
 
For a rescreened subject, the unique subject ID will be derived from the first-assigned subject number though he or she seems to have multiple subject numbers in eCRF records by screening assessment. The other subject numbers, which are to be recorded within a supplemental domain, will be associated with the unique subject ID.
 
			
Rescreening Subjects			

 
For rescreened subjects, data collected in screening-pass visit will be used for analysis. They may have multiple records at Screening and/or Day 1 visit, which associates with a screening-pass visit and screening failure visit(s)
 
Regarding a listing of SAEs in screening period, all pre-therapy SAEs captured in eCRF will be provided including screen failure records of rescreened subjects.
 
			
Study Treatment Start Date			
First randomized treatment start date			
Study Treatment Stop Date			
Latest end date of treatment			
• Note that the end date of treatment will be captured as the end date when subjects were intended to end the treatment, rather than when subjects have actually ended the treatment.			
Time Definitions (per GSK standard principles)			

 
1 week = 7 days
 
1 month = 30.4375 days
 
1 year = 365.25 days
 
			

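### The SAP's screening-pass rule has no exception for eye exams that the protocol lets rescreened subjects carry over from a failed screening, so Table 3.45 may omit their only pre-treatment exam

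*Protocol*

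**What the plan says.** **Protocol.** Section 5.3 allows repeated attempts at entry: "Subjects that fail screening are eligible to be rescreened up to 3 times". For a rescreened subject, "the re-exams of the ophthalmology at the rescreening are not required if the investigator judges it appropriate to use the previous screening result". Note 11 to Table 6 (Section 7.1) repeats the permission, "the previous result of ophthalmology exam at the screening may be used and the ophthalmology exam at the rescreening is not necessary", and attaches three conditions besides the investigator's judgement. The earlier exam must meet "There were no findings that would suggest a repeat ophthalmology exam performed within the next 3 months". There must be no new eye symptoms or complaints since that exam. And "The latest screening ophthalmology exam was performed within 3 months prior to anticipated Day 1".

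**SAP.** Appendix 2 copies the permission into its own Time & Events notes, without a derivation rule. Note [1] to the table in 10.3.1 says: "For rescreened subjects, data collected in screening-pass visit will be used for analysis". Section 10.6.1 states the same rule under Rescreening Subjects and, under Multiple Measurements at One Time Point, adds: "For multiple measurements at Screening and Day 1 visit, the screening-pass visit record will be used for analysis". The Rescreening Subjects entry makes one exception, for the listing of SAEs in the screening period, which also takes in failed-screening records.

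For the eye data, SAP 8.2.3.1 says: "Ophthalmology exam at screening and at on-therapy will be summarized separately". Appendix 14 assigns the screening exams to Table 3.45 and the on-therapy exams to Table 3.46, both on All Treated Subjects.

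**The concern.** The protocol lets an exam belonging to a failed screening serve as the subject's only pre-treatment eye exam. The SAP directs the analysis to the record of the screening that was passed, and under the waiver that visit need not contain an eye exam. The exam the investigator accepted can then fall outside the summary meant to show it.

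Proliferative retinopathy, macular edema and choroidal neovascularization are an adverse event category of special interest, and scheduled eye exams are a named mitigation in Protocol Appendix 2. The study has one arm and about 22 subjects, so the pre-treatment exam is the only within-study reference for what is seen on drug. At stake is whether Table 3.45 is complete, and whether it describes the same subjects as Table 3.46.

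**Working it through.** The plan states no figure on this point. The check is a cross-reading, followed by simple arithmetic for scale.

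**1. Can a treated subject have an eye exam only on a failed-screening record?** Yes. Protocol 5.3 and Table 6 note 11 waive the exam at rescreening when the conditions are met. No other pre-dose eye exam is scheduled.

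**2. Which record does the SAP use for that subject at Screening?** The screening-pass visit, under 10.3.1 note [1] and 10.6.1. The Rescreening Subjects entry goes on to say that several records may exist, but the rule itself does not depend on there being more than one. SAP Appendix 3 (10.3) keeps data at the nominal visit for which they were reported, so nothing moves an exam from one screening to another.

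**3. Is there an exception?** Only for the screening-period SAE listing. Ophthalmology is not mentioned.

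**4. Does the baseline definition help?** SAP 10.5.2.1 takes the latest assessment before dosing. Table 3.45 is built on the Screening time point, not on a baseline value, and no change from baseline is planned for eye exams. The baseline rule therefore does not govern this table.

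**5. Where is a carried-over exam recorded?** Protocol 7.4.7 says results go from worksheets to the eCRF. It does not say under which visit or subject number a reused exam is entered. The minimum data set for screen failures in Protocol 5.3 does not list ophthalmology.

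**6. Scale.** Inputs: 22 treated subjects (the planned enrolment, Protocol 4.3) and *k* subjects relying on an earlier exam. The documents do not give *k*, so it is an assumption. The share missing from Table 3.45 is *k*/22. If no findings were seen, the exact one-sided 95% upper bound with *n* = 22 − *k* is 1 − 0.05^(1/*n*).

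| *k* | *n* in Table 3.45 | Share missing | Upper bound, zero findings |
|---|---|---|---|
| 0 | 22 | 0.0% | 12.7% |
| 1 | 21 | 4.5% | 13.3% |
| 2 | 20 | 9.1% | 13.9% |
| 4 | 18 | 18.2% | 15.3% |
| 6 | 16 | 27.3% | 17.1% |

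**7. Can the direction of any distortion be known?** Let *a* be the rate of 'Yes' answers among fresh exams and *b* the rate among reused ones. The rate over all pre-treatment exams is [(22 − *k*)*a* + *kb*]/22.

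- If the table divides by subjects with an exam, it shows *a*. The difference is *k*(*a* − *b*)/22, which is positive when *a* > *b*.
- If the table divides by all 22, it shows (22 − *k*)*a*/22. The difference is −*kb*/22, which is never positive.

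The SAP's descriptive standard for categorical data (10.5.3) names N, n, frequency and percentage without saying which count is the divisor. As an illustration with assumed rates *a* = 40% and *b* = 10%, for *k* = 2, 4 and 6:

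- All pre-treatment exams: 8.2/22 = 37.3%, 7.6/22 = 34.5%, 7.0/22 = 31.8%.
- Table dividing by subjects examined: 40.0% each time, above those values.
- Table dividing by 22: 8.0/22 = 36.4%, 7.2/22 = 32.7%, 6.4/22 = 29.1%, below those values.

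The sign depends on a choice the plan does not state, and *a* and *b* have no source in the documents.

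**The case against.** The best defence has three parts.

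**Data entry.** The protocol treats the earlier result as usable for the new screening, and the exam may be done at any time between consent and first dose. If sites enter the accepted result under the rescreening visit, it is screening-pass data and nothing is lost. This stands as a possibility: the documents neither require nor exclude it. The loss is therefore conditional.

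**A tie-break rule.** The multiple-measurements sentence applies where several records compete, and the SAP's change log describes the added text in that way. A subject with one eye exam has no tie to break. This fits that sentence. It does not fit the Rescreening Subjects entry, which is not conditioned on duplicates. The SAE exception written beside that entry suggests the rule was understood to leave out failed-screening records.

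**Limited consequence.** Even on the literal reading, only one summary is touched. Listing 57 covers ophthalmologic exams, and Table 3.46 with its worst-case count uses exams after screening. This stands.

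A reader might go further and infer that the missing exams come from cleaner eyes, that the screening percentage is therefore too high, and that new findings on drug could be hidden. The documents do not support this. Absence of a finding calling for a repeat exam within three months is not the same as a 'No' to every exam question; a stable chronic finding could qualify. The direction of any shift depends on the unstated divisor. No screening-to-on-therapy comparison is planned for eye exams. AESIs are identified by case-by-case review at patient level (SAP 10.6.4), which does not use the percentages in Table 3.45.

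**Conclusion.** The gap is real and narrow. As written, the SAP's rule for rescreened subjects does not accommodate the protocol's eye exam waiver. Taken literally, Table 3.45 omits the only pre-treatment eye exam of any subject who used the waiver, while that subject's on-therapy exams enter Table 3.46.

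This rests on two assumptions: that at least one treated subject used the waiver, and that the accepted exam was not re-entered under the rescreening visit. Neither can be checked from the documents. The number affected may be zero; each affected subject would be 4.5% of 22. No size or direction can be given for an effect on the screening percentages. Listing 57, Table 3.46 and AESI review are not shown to be affected, and the primary Hgb analysis is not involved. This is a point of completeness and traceability in one safety table, worth settling because it is cheap.

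**What to change.** - In SAP 10.3.1 and 10.6.1, add an exception for ophthalmology: the Screening value is the latest eye exam before the first dose, including one on a screening-failure record that was accepted under Table 6 note 11.
- Link the records through the unique subject ID that SAP 10.6.1 already defines.
- Footnote in Table 3.45 the number of subjects whose exam was reused.
- Confirm under which visit and subject number the eCRF holds a reused exam, so that the programming finds it and does not count it twice.

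The cost is a short SAP amendment, one programming exception and a footnote. No new exam is needed, and no new data either, provided the accepted exam is in the eCRF. The conditions for reusing an exam do not change.

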5.4. Withdrawal Criteria

If subjects meet one of the following criteria, study treatment should be permanently discontinued and withdrawal reason should be recorded.

- Hgb <7.5 g/dL
Note: HemoCue Hgb values will be employed. If an initial Hgb value meets the Hgb stopping criteria, measurement will be repeated at the same study visit (using the same sample) to calculate the average. If the average meets the Hgb stopping criteria, study treatment will be discontinued.
- Kidney transplant
- Subject becomes pregnant or intends to become pregnant during the study.
- Diagnosis of new or recurrent cancer
- Liver chemistry abnormalities exceeding the threshold criteria (see Section 5.4.1.)
- Need for chronic (more than 14 days) use of prohibited medication (strong inhibitors/ inducers of CYP2C8 meet this criteria)
- When the investigator (or subinvestigator) considers necessary to withdraw the subject from the study for other reasons

Subjects who meet any of the withdrawal criteria or are withdrawn for other reasons during the treatment phase should be assessed at withdrawal visit after study treatment is discontinued, and will then enter the follow-up phase.

Should a subject fail to attend a required study visit, the investigator (or subinvestigator) should take the following measures:

- The investigator (or subinvestigator) or designee should attempt to contact the subject and reschedule the missed visit as soon as possible.
- The investigator (or subinvestigator) should counsel the subject on the importance of maintaining the assigned visit schedule and determine whether the subject is willing to continue his/her participation in the study and/or whether the subject should remain in the study.
- The investigator (or subinvestigator) or designee should make every effort to regain contact with a subject who is deemed “Lost to Follow-up”. All efforts to contact the subject should be documented in the subject’s clinical charts.
- Should the subject continue to be unreachable, then and only then will he/she be considered “Lost to Follow-up.”

[figure not shown]
A subject may withdraw from the study at any time at his/her own request. The investigator (or subinvestigator) may withdraw a subject from the study at any time for safety or compliance reasons or study conduct considerations. If a subject withdraws from the study, he/she may request destruction

of any clinical samples taken, and the investigator (or subinvestigator) must document this in the site study records.

[figure not shown]
5.4.1. Liver Chemistry Stopping Criteria

Liver chemistry stopping and increased monitoring criteria have been designed to assure subject safety and evaluate liver event etiology (in alignment with the Food and Drug Administration [FDA] premarketing clinical liver safety guidance).

Liver Chemistry Stopping and Increased Monitoring Algorithm

Liver Chemistry Increased Monitoring Algorithm with Continued Therapy for ALT $\geq 3 \times \text{ULN}$ but $< 8 \times \text{ULN}$

Liver Safety Required Actions and Follow up Assessments can be found in Section 12.5.

5.4.1.1. Study Treatment Restart or Rechallenge

Study treatment restart or rechallenge after liver chemistry stopping criteria are met by any subject participating in this study is not allowed.

5.5. Subject and Study Completion

A completed subject is one who has completed all periods of the study including the follow-up visit. The study will be completed with the last subject's last study visit.

6. STUDY TREATMENTS

6.1. Investigational Product and Other Study Treatment

The term 'study treatment' is used throughout the protocol to describe any products received by the subject as per the protocol design.

The study drug GSK1278863 will be supplied as fast-release film coated tablets for oral administration containing 1 mg, 2 mg, 4 mg, or 6 mg of GSK1278863 (Table 2). There are two sizes of GSK1278863 tablets.

Table 2 Description of GSK1278863 Tablets

GSK1278863 tablets of specific content	Description
1 mg tablets, 2 mg tablets, 4 mg tablets	7.0 mm round, standard biconvex, white film coated tablets containing 1 mg, 2 mg, or 4 mg of GSK1278863 as active ingredient
6 mg tablets	9.0 mm round, standard biconvex, white film coated tablets containing 6 mg of GSK1278863 as active ingredient

GSK1278863 tablets of specific content are packed in high density polyethylene (HDPE) bottles, with 35 tablets per bottle. Subjects are to take one to four tablets (Table 3) with water once daily according to the dose level indicated at each study visit. Subjects can take GSK1278863 tablets without regard to food or hemodialysis. The administration schedule (starting dose and dose adjustment) described in Section 6.3. should be followed.

Table 3 Dose Levels of GSK1278863 and Number of Tablets Taken

Dose level of GSK1278863 (once daily)	1 mg	2 mg	4 mg	6 mg	8 mg	12 mg	18 mg	24 mg
Number of GSK1278863 tablets taken	1 mg tablet ×1	2 mg tablet ×1	4 mg tablet ×1	6 mg tablet ×1	4 mg tablet ×2	6 mg tablet ×2	6 mg tablet ×3	6 mg tablet ×4

Subjects should be instructed to bring GSK1278863 tablets with bottles at each study visit, and all unused GSK1278863 tablets will be collected from subjects at each study visit.

6.2. Treatment Assignment

This is an open-label, non-comparative study. All eligible subjects will take GSK1278863. Refer to Study Reference Manual (SRM) regarding details such as allocation of randomization number.

6.3. Treatment Schedule

Starting dose (Day 1 to Week 4)

In the Japanese HD patients not using ESAs enrolled in the study, oral administration of GSK1278863 once daily at the starting dose of 4 mg will be started (Day 1), and continued until the day of Week 4.

Maintenance Dose (Week 4 to Week 24)

From Weeks 4 to 24, interruption of treatment or dose adjustments will be made within the maintenance dose range of 1-24 mg (Table 4) according to the dose adjustment algorithm (Table 5) to achieve and/or maintain Hgb within the target range (10.0-12.0 g/dL) based on the HemoCue Hgb value measured every 4 weeks. Dose changes will be made every 4 weeks. If any of the one-step dose reduction criteria is met during treatment at the minimum maintenance dose (1 mg), treatment should be interrupted; once the one-step dose increase criteria are met, treatment at 1 mg will be resumed. If the one-step dose increase criterion is met during treatment at the maximum maintenance dose (24 mg), treatment at 24 mg should be continued.

Table 4 Maintenance Dose of GSK1278863

Dose step	1	2	3	4	5	6	7	8
Dose level of GSK1278863 (once daily)	1 mg	2 mg	4 mg	6 mg	8 mg	12 mg	18 mg	24 mg
Number of GSK1278863 tablets taken	1 mg tablet ×1	2 mg tablet ×1	4 mg tablet ×1	6 mg tablet ×1	4 mg tablet ×2	6 mg tablet ×2	6 mg tablet ×3	6 mg tablet ×4

Table 5 Dose Adjustment Algorithm (GSK1278863)

Hgb (g/dL)	Hgb increase over 4 weeks (g/dL)	Treatment
>13.0	NA	Interrupt treatment until Hgb decreases to less than 12.0 g/dL Resume treatment at the one lower dose level (resume treatment at 1 mg once the one-step dose increase criteria are met, if interrupted at 1 mg)
12.0-13.0	NA	One-step dose reduction
10.0-<12.0	>2.0	One-step dose reduction
	≤2.0	Continue treatment at the current dose level
7.5-<10.0	>2.0	One-step dose reduction
	0.5-2.0	Continue treatment at the current dose level
	<0.5	One-step dose increase
<7.5	NA	Discontinue treatment permanently * and initiate another appropriate treatment

*: If an initial Hgb value is less than 7.5 g/dL, measurement will be repeated at the same study visit (using the same sample) to calculate the average. If the average meets the Hgb stopping criteria, study treatment will be discontinued.

6.4. Blinding

This is an open-label study.

6.5. Packaging and Labeling

The contents of the label will be in accordance with all applicable regulatory requirements.

6.6. Preparation/Handling/Storage/Accountability

- No special preparation of study treatment is required.

- Only subjects enrolled in the study may receive study treatment and only authorized site staff may supply study treatment. All study medications must be stored in a secure environmentally controlled and monitored (manual or automated) area in accordance with the labeled storage conditions with access limited to the investigator (or subinvestigator) and authorized site staff.
- Subjects must bring all of supplied study medication bottles of GSK1278863 at each study visit. Study staff will collect all of study medication bottles supplied at the previous study visit and supply new study medication bottles.
- The investigator (or subinvestigator), institution, or the head of the medical institution (where applicable) is responsible for study treatment accountability, reconciliation, and record maintenance (i.e. receipt, reconciliation and final disposition records).
- Under normal conditions of handling and administration, study medication is not expected to pose significant safety risks to site staff. GSK will provide an information related to occupational hazards and recommended handling precautions either to the investigator (or subinvestigator) when necessary or upon request of the medical institution.
- Further details are provided in the SRM.

